Compare the serologic responses to cell culture-based quadrivalent influenza vaccine (ccIIV [Flucelvax]) versus live attenuated quadrivalent influenza vaccine (LAIV [FluMist]) in a randomized controlled trial (RCT) among racially diverse children/young adults 4-21 years of age. The primary endpoint is change in antibody titer. The secondary Aims are to: 1. Compare the immune responses between ccIIV and LAIV; 2. The nasal microbiome may both effect and be affected by vaccination (2019 only);

Methods: An unblinded, randomized controlled trial will be conducted by Pediatric and Family Medicine teams at the UPMC and the University of Pittsburgh. Randomization to either LAIV or ccIIV on a 1:1 ratio will be done in blocks of 4. Depending on funding, up to 240-260 will be randomized; assuming a 16% drop-out rate (21% in children under 9 and 11% in ages 9 and up) this would result in approximately 200 participants. Efforts will be made to recruit/include children 4-8 years and persons not vaccinated in 2019-20 for comparison of immune response to those previously vaccinated in 2019-20. Young persons aged 4-21 years without a contraindication to LAIV who plan to receive seasonal influenza vaccination at one of our recruiting sites are eligible to participate. The primary endpoints are change in antibody titers. Given that LAIV is known to produce limited IgG [4], other potential beneficial responses to nasal administration of intranasal LAIV compared to ccIIV will be examined as secondary endpoints, including changes in serum IgA. Titer levels will be log transformed and reported as seropositivity, mean fold rise (MFR) and seroconversion. Specimens will be collected on a subset of participants for cell-mediated immune responses to be studied at CDC and Pitt.

Introduction

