Compare the serologic responses to cell culture-based quadrivalent influenza vaccine (ccIV [Flucelvax]) versus live attenuated quadrivalent influenza vaccine (LAIV [FluMist]) in a randomized controlled trial (RCT) among racially diverse children/young adults 4-21 years of age. The primary endpoint is change in antibody titer.

a. Serology—based on hemagglutination inhibition assay (HAI) titers: Hypotheses: Mean fold rise (MFR) based on HAI titers and seroconversion will differ between LAIV and ccIV.

Secondary Aims:

1. Compare the immune responses between ccIV and LAIV.
2. The nasal microbiome may both effect and be affected by vaccination (2019 only)

B. Study Design and Methods

B.1 Study Design and population Years 1 and 2 combined

1. Total number of subjects to be enrolled at this site up to 480 enrolled over two years (of up to 650 screened)
2. Describe and explain the study design:
This study will be an unblinded randomized controlled trial of 200-220 (2019) and up to 260 (2020) children, adolescents and young adults to examine their immune response following influenza vaccination. For 2020, all participants will have a baseline draw and a Day 28 (range 21-35 days) blood draw. A subset of up to 120 participants ages 9-21 **only** will have a blood draw on Day 7 (range 6-9 days)
3. Describe the primary and secondary study endpoints:
Primary:
-Seroconversion based on hemagglutinin inhibition (HAI) titers
Secondary:
- Day 0 and Day 28 Seroprotection based on HAI titers
- Day 0 and Day 28 geometric mean comparisons of HAI titers

The overall purpose is to understand immune responses related to influenza vaccination and their determinants. We will also look at serum IgG and IgA, cell mediated immunity indices, transcriptomics, genomic, protonomic, cell-mediated immunity, nasal microbiome (2019 only) and/or past vaccine experience effects on the immune response to influenza vaccination.

B.2 Study Design and Population Year 2 2020-2021 only

This study will be a randomized controlled trial of up to 260 children, adolescents and young adults to examine their immune response following influenza vaccination. All participants will have a blood draw at baseline and at Day 28 (range 21-35 days). A subset (up to 120) of participants ages 9 -21 will have a blood draw at Day 7 (range 6-9 days).

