IgD, CD95, CD11b, CD38, CD57, CD27, CD123, CD127, HLADR, KLRG1, CD45R0, CD154. With this panel we can identify granulocyte, monocyte, and lymphocyte subsets with high resolution. For example, this panel allows for identification of CD8+ T cells, NKT cells, CD4+ T cells, B cells, NK cells, and lineage negative ILC, further segregated by activation and memory markers. All of this information is derived from a single flow cytometry run on 5×10^6 cells.

Data are analyzed by multidimensional algorithms such as t-stochastic neighborhood embedding (tSNE) or sequential pattern discovery using equivalence classes (SPADE) to cluster cell types based on the full panel of antigens stained rather than typical two dimensional staining analyses. tSNE works by first creating a probability distribution that dictates the relationships between various neighboring data points in high-dimensional space. It then tries to recreate a low dimensional space (two dimensional plot) that follows that probability distribution as best as possible to segregate cells based on similarity of marker expression. SPADE uses a similar approach to determine relationships between individual cells, but relays this information as a two dimensional branching tree plot that indicates the degree of similarity between cells. These algorithms allow for identification in three dimensions of overlapping cell subsets in two dimensional space and consideration of multiple stains at the same time, with the potential to identify new cell subsets.

C. Statistical Analysis

Pre- and post- vaccination geometric mean antibody titers (GMT) will be \log_2 transformed and compared among participants who received LAIV or cclIV. The mean fold rise, seroconversion and seropositivity at Day 28 will be calculated.

Seroconversion will be defined as either a pre-vaccination HAI titer $<1:10$ and a post-vaccination HAI titer $\geq 1:40$ or a pre-vaccination HAI titer $\geq 1:10$ and a minimum four-fold rise in post-vaccination HAI antibody titer.

Fold-rise in HAI titers is the ratio of Day 28 log titers to Day 0 log titers and will be conducted with baseline titer as a covariate.

C.1 Power Analyses

Using a power calculation for a Chi square test with alpha set at 0.05 reveals the following:

Effect size	Final sample size	Power	Comments
0.3	90	.81	Fairly large effect size; unlikely to occur
0.3	81	.77	Fairly large effect size; assumes 10% failure to complete
0.1	81	.15	No power for small effect size

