0.2	200	.81	Good power for moderate effect size
0.1	200	.29	No power for small effect size

<https://www.anzmtg.org/stats/PowerCalculator/PowerChiSquare>

If funding is available for the full sample, analyses based on prior 2019-20 vaccine history (none, egg-based, cell-based) will provide additional insight into vaccine immunogenicity.

D. Human Subjects

D.1. Consent

Participants in this study will provide written consent (parents and young adults) and assent (children/teens) as applicable for specimen collection, influenza vaccination, and medical record review.

Further details regarding data privacy and protection of human subjects are provided in the IRB application document.

D.2. Participant Compensation

Participants will be compensated for each visit:

- First visit = \$35 plus \$5 travel for a total of \$40
- Second visit on subset = \$25 plus \$5 travel for a total of \$30
- Final visit = \$45 plus \$5 travel for a total of \$50

The maximum possible payment will be \$90 (two visits)-\$120 (three visits). If a separate vaccine visit is required, participants will be paid \$30 for the blood draw and enrollment visit and \$10 for a separate vaccine visit.

D.3. Threats to study and contingencies

In the event of a late start, some aspects of recruitment may be impacted: (1) PBMCs are time-consuming to process, leading to a limited throughput; thus, the sample size for PBMCs is constrained by starting later. (2) vaccination in the community is likely to start early, due to vaccination by community pharmacies and to mass purchase by UPMC; later recruitment is more difficult because some will have already been vaccinated.

Contingency plans: In the event of a late start, several contingencies will be used. First, a greater emphasis will be given to recruiting young adults, who are less likely to have been vaccinated early. Second, if one vaccine is delayed, then persons may be recruited per the randomization scheme and those randomized to the missing vaccine may have their baseline blood drawn but be asked to return for the rest of the study once the vaccine is available. Third, given that quality processing of the PBMCs is time consuming with limited throughput, overall target sample sizes may be reduced.

D.4 Timeline

	Aug	Sept- Nov	Dec	Jan	Feb-May	June-July
Prep, Supplies, Train						
Enroll, vaccinate, draw blood, process specimens						
Organize and ship to CDC (or Battelle) lab						
Conduct initial HAI						
Advanced Lab assays						

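### The Primary Aim names change in HAI titer, but B.1 makes only seroconversion primary and C.1 powers only a chi-square test; the power cost depends on the response pattern

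*Combined protocol and SAP*

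**What the plan says.** The combined protocol and SAP describes the primary endpoint in two ways.

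- The Primary Aim (Section A) says "The primary endpoint is change in antibody titer". The Methods paragraph of the opening summary says "The primary endpoints are change in antibody titers".
- The hypothesis under the Primary Aim names two measures: "Mean fold rise (MFR) based on HAI titers and seroconversion will differ between LAIV and ccIV".
- B.1 item 3 lists a single primary endpoint, "Seroconversion based on hemagglutinin inhibition (HAI) titers". Its secondary list includes "Day 0 and Day 28 geometric mean comparisons of HAI titers".

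Section C defines seroconversion as a cut of the paired titers: from below 1:10 to at least 1:40, or "a pre-vaccination HAI titer $\geq 1:10$ and a minimum four-fold rise in post-vaccination HAI antibody titer". It also plans to compare log2 titers between the vaccines and to analyse fold rise with baseline titer as covariate.

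C.1 opens with "Using a power calculation for a Chi square test with alpha set at 0.05 reveals the following". All five rows of its table belong to that test. There is no row for a titer analysis, no SD of log2 titer and no assumed seroconversion rate in either arm.

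**The concern.** The question in the aim is how far titers move. The endpoint in B.1 records only whether each participant crossed a threshold, so a two-fold rise counts as no rise and a 64-fold rise counts as a four-fold one. The documents give no reason for preferring the cut.

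Two things are at stake. First, a reader cannot tell which result decides the trial, because the aim and the endpoint list give different answers. Second, the sample-size case rests wholly on the binary version, which may be the less efficient one. This matters because the plan expects recruitment pressure: B.2 foresees enrollment losses for each week of a shortened season, and D.3 allows target sizes to be reduced. C.1 itself describes the row for effect size 0.1 at 200 participants as "No power for small effect size".

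**Working it through.** **Inputs from the documents.** Chi-square test, alpha 0.05; effect size w = 0.2 with N = 200 and stated power .81 (C.1); 1:1 allocation and about 200 evaluable participants (opening summary: 240 × 0.84 = 201.6). So n = 100 per arm.

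**Step 1: the plan's figures.** Power = P(χ²₁(λ) > 3.84), with λ = N·w².

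| w | N | Stated | Recomputed |
|---|---|---|---|
| 0.3 | 90 | .81 | .812 |
| 0.3 | 81 | .77 | .770 |
| 0.1 | 81 | .15 | .147 |
| 0.2 | 200 | .81 | .807 |
| 0.1 | 200 | .29 | .293 |

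All five rows reproduce with one degree of freedom, that is, a 2×2 table. With two degrees of freedom the fourth row would be .718, so the table is for a binary outcome in two arms.

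**Step 2: the same effect on the titer scale, normal shift.** Assumption: log2 change is normal with equal SD in both arms, and seroconversion is treated as a single cut of it. The documents give no rates, so the mean rate p̄ is varied. For equal arms, p₁ − p₂ = 2w√(p̄(1 − p̄)). The standardized difference is D = Φ⁻¹(p₁) − Φ⁻¹(p₂). Power is that of a two-sample t-test with 100 per arm and noncentrality D√(100/2).

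| p̄ | p₁ v p₂ | D | Titer power | Points above .807 |
|---|---|---|---|---|
| 0.2 | .280 v .120 | 0.592 | .986 | 17.9 |
| 0.3 | .392 v .208 | 0.537 | .966 | 15.9 |
| 0.4 | .498 v .302 | 0.514 | .951 | 14.4 |
| 0.5 | .600 v .400 | 0.507 | .946 | 13.9 |

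The table is symmetric about 0.5. At p̄ of 0.1 or 0.9 the difference is 19 points. Under this model, 92 (p̄ = 0.2) to 126 (p̄ = 0.5) evaluable participants would give the titer analysis power of .81. At w = 0.1 its power is .53 to .42 over the same range of p̄, against .29.

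**Step 3: realistic titers, still a shift.** Titers were simulated with 100 per arm, in two-fold dilutions with a floor below 1:10. The protocol's own seroconversion rule was applied, and the gap between arms was set to give w of about 0.2. Chi-square power was .81 to .83, the t-test on log2 rise .92 to .98, and the baseline-adjusted analysis .93 to .99. The gain was about 10 to 17 points. At seroconversion of 49% v 30%, for example, power was .82 for chi-square, .92 for the t-test and .96 with baseline adjustment.

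**Step 4: a different response pattern.** Here the vaccines differ in the share of participants who respond strongly, and non-responders stay flat. Chi-square power was .80 to .83 and titer power .73 to .92.

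- Least favourable to the titer analysis (seroconversion 25% v 10%): .829 v .728 baseline-adjusted, 10 points worse.
- Most favourable (31% v 15%): .829 v .921 baseline-adjusted, 9 points better.

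**The case against.** A reader might infer three stronger things, and the documents do not support them.

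1. *That seroconversion is settled as the primary endpoint.* It is the sole primary only in B.1; the opening summary and the Primary Aim say otherwise. The firm finding is the disagreement, together with power for one side only.
2. *That the plan loses 10 to 18 points of power outright.* That range needs the normal shift with equal SD. The plan does not assume a responder pattern, but it does not assume a shift either. It gives some reason to expect mixed responses: the opening summary says LAIV is known to produce limited IgG, the Introduction says pre-existing memory differs with exposure, and B.2.2 mixes a returning vaccinated cohort with new recruits of differing vaccination history. None of this proves an all-or-none response, but Step 4 belongs in the range.
3. *That the cut throws away most of the titer information.* Even under the shift model, matching .81 takes 92 to 126 participants instead of 200. The cut therefore keeps roughly 92/200 = 46% to 126/200 = 63% of the information.

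The other side is also right that Section C already plans most of the titer analysis, that C.1 has .81 for a moderate effect, and that the titer analysis would still fall well short of 80% at w = 0.1. Choosing a responder rate over a titer ratio is partly a choice of question. What survives is that the plan's own aim has made that choice, in favour of titer change, and its endpoint list and power section do not follow it.

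**Conclusion.** The concern holds in a conditional form. It is certain from the text that the primary endpoint is stated inconsistently and that the measure named in the Primary Aim has no power calculation. The size of the power difference is not certain. The titer analysis gains about 10 to 18 points at N = 200 if log2 change is roughly normal with equal SD, and the difference runs from about −10 to +9 points if the vaccines differ mainly in the share of responders. Both ranges rest on assumed seroconversion rates and simulated titers, because the documents supply neither rates nor an SD.

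This is an inexpensive improvement, not a flaw that invalidates the trial. The main reason to re-rank is agreement with the stated aim; the likely gain in power is a second, conditional reason.

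**What to change.** - **Opening summary, Primary Aim, B.1 item 3 and Section C:** make them agree on change in HAI titer as primary. For each vaccine strain, estimate the LAIV v ccIIV difference in Day 28 log2 titer adjusted for Day 0 log2 titer. Report 2 to the power of that difference as a geometric mean titer ratio with 95% CI.
- **Strains:** both vaccines are quadrivalent, so state how the four strain results are handled, for example which of them decide the primary question and whether alpha is shared.
- **Seroconversion:** keep the present definition and make it the first secondary endpoint. This covers the case where response is close to all-or-none.
- **C.1:** add power or the detectable titer ratio at the planned final N, with a stated SD. The pooled SD from the 2019 season would serve, taken without using arm differences. For an unadjusted comparison of log2 change with 100 per arm and 80% power, the detectable difference is about (1.96 + 0.84) × SD × √(2/100) = 0.396 × SD. As an illustration only, SDs of 1.5 and 1.8 give ratios of 2^0.594 = 1.51 and 2^0.713 = 1.64.
- **Section C:** the fold-rise sentence describes a ratio of log titers. On the log scale a fold rise is a difference, so the sentence should be corrected if it stays.

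**Cost:** wording and one recalculated table, with no new participants, samples or assays. The trial is unblinded and its 2019 season has been enrolled, so the date and reason for the change must be recorded, with a statement that it was made without sight of 2020 results by arm. A titer ratio is less familiar to clinicians than a seroconversion rate, and there is no gain in power if response is all-or-none.

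### The between-arm Day 28 GMT comparison has no stated baseline covariate, and Day 0 titers are listed as an outcome although they precede vaccination

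*Combined protocol and SAP*

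**What the plan says.** Section B.1, item 3 gives seroconversion as the primary endpoint and lists two secondary endpoints: "Day 0 and Day 28 Seroprotection based on HAI titers" and "Day 0 and Day 28 geometric mean comparisons of HAI titers". It does not name the contrast, the test or the model for either.

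Section C supplies the contrast for the GMTs. Pre- and post-vaccination values are to be log2 "transformed and compared among participants who received LAIV or cclIV", which is a comparison by vaccine at each time point. No covariate appears in that sentence. Seropositivity at Day 28 is to be calculated, again without a model.

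Baseline titer enters the plan in two other places:

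- Section C defines fold rise as the Day 28 log titer divided by the Day 0 log titer, "and will be conducted with baseline titer as a covariate".
- Seroconversion is built on the pre/post pair. For those with a detectable baseline it requires "a pre-vaccination HAI titer $\geq 1:10$ and a minimum four-fold rise in post-vaccination HAI antibody titer".

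Section B.2.4.1b places vaccination after the pre-vaccination blood draw, and Section B.2.4.1a allocates participants 1:1 in blocks of four.

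**The concern.** There are two separate issues.

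**Day 28.** Section B.2.2 expects about half of the 2020 participants to return from the cohort vaccinated in 2019-20. Among new recruits aged 9-21, it gives priority to those not vaccinated that season. The Introduction says that prior exposure shapes response. Day 0 titers are therefore likely to vary widely and to predict Day 28 titers. A Day 28 comparison without Day 0 in the model leaves that predictable variation in the error term. No stratification by prior vaccination or age is stated that would remove some of it by design.

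**Day 0.** The sample is drawn before vaccination in arms formed by randomization. Any Day 0 difference between the arms as randomized is chance. Listing it among the outcome endpoints invites a p-value with no bearing on vaccine effect, and an occasional small p-value that could be misread.

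At stake are the precision of one secondary estimate and the clarity of the endpoint list.

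**Working it through.** **Inputs from the documents**

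- Final N = 200, from the full-sample rows of the power table in C.1. With 16% drop-out, 240 to 260 randomized gives 240 × 0.84 = 201.6 to 260 × 0.84 = 218.4, which is consistent with this.
- 1:1 allocation, hence 100 per arm.
- Four strains, since both vaccines are quadrivalent and HAI is run against the vaccine strains (B.3.1).
- Alpha 0.05.

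**Inputs assumed**

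- The within-arm correlation r of Day 0 and Day 28 log2 titers, taken as 0.4 to 0.7.
- For the power illustration only, a true difference of 0.4 SD in log2 titer. The documents give no SD and no correlation.

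**Step 1: the plan's own figures.** C.1 describes its method as "Using a power calculation for a Chi square test with alpha set at 0.05". Power is the upper tail of a noncentral chi-square with noncentrality N × w². With 1 degree of freedom every row reproduces:

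| w | N | stated | recomputed |
|---|---|---|---|
| 0.3 | 90 | .81 | 0.812 |
| 0.3 | 81 | .77 | 0.770 |
| 0.1 | 81 | .15 | 0.147 |
| 0.2 | 200 | .81 | 0.807 |
| 0.1 | 200 | .29 | 0.293 |

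The table concerns a test of proportions. It contains no figure for the GMT endpoint, so nothing below changes it.

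**Step 2: precision of the Day 28 contrast.** Adjusting for Day 0 multiplies the variance of the between-arm difference by 1 − r². The equivalent unadjusted sample size is 200 / (1 − r²). The last two columns assume a difference of 0.4 SD and two-sided alpha 0.05.

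| r | 1 − r² | variance cut | N = 200 acts like | power, 100 per arm | n per arm for 80% |
|---|---|---|---|---|---|
| unadjusted | 1 | – | 200 | 80.7% | 99 |
| 0.4 | 0.84 | 16% | 238 | 87.0% | 83 |
| 0.6 | 0.64 | 36% | 312 | 94.2% | 63 |
| 0.7 | 0.51 | 49% | 392 | 97.7% | 51 |

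**Step 3: does the fold-rise analysis already supply this?** Let Y0 and Y1 be the Day 0 and Day 28 log2 titers and T the arm.

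- If fold rise were a difference of logs, Y1 − Y0 = a + bT + gY0 rearranges to Y1 = a + bT + (1 + g)Y0. The arm effect b is then the same as in ANCOVA on Day 28.
- As written, the outcome is Y1 / Y0. Then Y1 / Y0 = a + bT + gY0 gives Y1 = aY0 + bTY0 + gY0², in which the arm effect is multiplied by the baseline. This is a different contrast.
- A numerical check: rises from 10 to 40 and from 40 to 160 are both four-fold, a log2 difference of 2 in each case. The ratios of logs are log 40 / log 10 = 1.60 and log 160 / log 40 = 1.38.

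So the fold-rise model as worded does not deliver the adjusted Day 28 GMT ratio.

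**Step 4: Day 0.** If the Day 0 GMT were tested between arms for each of four strains at 0.05, the chance of at least one false positive under independence is 1 − 0.95⁴ = 0.185.

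**The case against.** The strongest reply is that the plan already uses baseline where it matters. The primary hypothesis is that "Mean fold rise (MFR) based on HAI titers and seroconversion will differ between LAIV and ccIV". Seroconversion is defined from the pre/post pair, and fold rise carries the baseline covariate. Under the usual difference-of-logs meaning, that fold-rise model is the ANCOVA asked for here under another name, so little precision would be lost to the trial. This is largely right about intent. A reader might infer that the plan throws baseline away, and the documents do not support that. What remains is that the text defines fold rise as a ratio of logs, for which the equivalence fails, and that the fold-rise model does not cover seroprotection.

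The second reply is that no Day 0 significance test is specified. The endpoint line taken alone could even mean a within-arm comparison of Day 0 with Day 28. Section C points to a comparison by arm, but it names no test, so Day 0 may be intended as descriptive. This stands, and the 18.5% is therefore conditional on testing. A reader might go further and count eight Day 0 tests (four strains by two endpoints), for 1 − 0.95⁸ = 34%. Section C describes only GMTs as compared before vaccination, so four contrasts is the most the text supports. Seroprotection is also a dichotomy of the same titers, so eight tests would not be independent.

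Third, a Day 28 comparison without a covariate is unbiased under randomization. This also stands: the cost is precision and not validity. The documents do not say that the comparison will be unadjusted. They state no covariate.

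**Conclusion.** The point holds as a minor one. For the Day 28 GMT, the plan states a by-arm comparison without the Day 0 value, although that value is already collected and using it would cost nothing. Under assumed correlations of 0.4 to 0.7 the variance could be 16% to 49% lower. This rests on a roughly linear relation with a similar correlation in both arms, and the true value is unknown from the documents.

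The 1 − r² factor applies to mean log titer. It should not be carried over to binary seroprotection, for which no gain is quantified here.

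Day 0 GMT and seroprotection do not belong among the outcome endpoints, because in the arms as randomized they can differ only by chance. It would be too strong to say that the plan commits to meaningless tests, that the Day 28 result would be biased, or that the sample size or stated power is affected.

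**What to change.** - Restate the secondary endpoint as the Day 28 GMT ratio between arms for each strain, estimated by ANCOVA on log2 titer with Day 0 log2 titer as covariate and back-transformed as 2 to the power of the adjusted difference.
- Report Day 0 GMT and seroprotection by arm as descriptive baseline data, without a test.
- If Day 28 seroprotection is also adjusted for Day 0 log2 titer, report a standardized (marginal) risk difference: average the model's predicted risks over all participants under each arm and subtract. A conditional odds ratio from a logistic model would change the quantity estimated.
- If fold rise is reworded as a difference of log2 titers, say that its baseline-adjusted arm contrast is the same as the one above, so that the two are not presented as separate findings.

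The cost is a change of wording in Section B.1, item 3 and Section C. It needs no new samples, visits or assays, and the sample size and power table stay as they are.

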Approximately $\frac{1}{2}$ of the subjects would be recruited from our returning 2019-2020 vaccinated cohort of patients with three prior visits. Among non-cohort recruits, we will prioritize persons ages 4-8 years regardless of 2019-20 vaccination status and persons 9-21 years who were not vaccinated with seasonal influenza vaccine in the 2019-20 season. Enrollment in this study will begin after IRB and CDC approval is obtained and will continue until the target sample size for each group is reached with the goal of completing all baseline study visits by mid November of the current year. We will recruit from primary care and pediatric locations such as UPMC Shadyside Family Health Center; Children's Community Pediatrics (CCP) Primary Care Oakland; and, perhaps, East Liberty Family Health Center. We will also recruit past participants who were vaccinated at Falk Pharmacy. Because the Pitt+Me database was highly successful in 2019-20, we will use it to recruit new participants. Inclusion of older teenagers and young adults aged 18-21 years allows for college students using Falk pharmacy, as well as returning cohort members.

B.2.4 Enrollment procedures: Data and Blood Sample Collection

B.2.4.1a Enrollment visit

Eligible patients who agree to enroll will be consented prior to conducting further baseline visit enrollment procedures. Written informed consent includes permission to access medical records and/or state registry records to obtain data related to medical history, medication use, vitals, high-risk codes, and vaccination history.

A survey of demographics and health status will be collected at baseline, or if insufficient time, at a follow-up study visit. Data will be entered directly into REDCap (or if collected via paper will be entered into REDCap post-hoc.)

All participants will have blood drawn at baseline enrollment visit (may be done during the summer prior to vaccination). Refer to Table for blood volumes and tube types to be collected. The total blood volume for a particular participant is based on several factors including size of the participant's veins, limitations on number of PBMC specimens that the lab can process in a particular day, past PBMC yield from the participant (if known), enrollment site, past vaccination status, and courier transportation availability, given the need to process PBMCs quickly.

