Upon consent, participants will be randomized to one of two vaccine types (LAIV or cclIV) using a 1:1 computer generated simple randomization scheme. Randomization block size will be conducted in sets of four (2 LAIV and 2 cclIV).

Table. Specimens to be collected for 2020

Age Group	Blood tube type	Day 0 visit	Day 7 post vax visit	Day 28 post vax visit	Total
4-8 years	SST Serology	5-10 mL	No visit	5-10 mL	10-20 mL
	CPT-PBMCs	4 mL	No visit	4 mL	8 mL
9-21 years	SST Serology	10 mL	--	10 mL	20 mL
	CPT-PBMCs on subset	24 mL	24 mL	24 mL	72 mL

B.2.4.1b Vaccination visit

All participants will receive influenza vaccine after the pre-vaccination blood draw according to their randomized influenza vaccine allocation. Both vaccines are FDA approved, licensed and recommended for these age groups. Vaccinations will be recorded in the EMR and Vaccine Information Sheets will be provided following standard clinical protocol. This visit may occur at the time of the enrollment visit provided that the vaccine to which the participant is randomized is available.

B.2--4.1c Blood draw procedures

All blood will be collected by trained personnel with experience drawing blood from children. The blood samples will be collected using Vacutainer tubes, appropriate for type of processing, and appropriately labeled with a uniform scheme (including study ID and collection time point).

Serum specimens will be aliquoted and frozen. Individual aliquots will be either shipped to CDC for analysis, analyzed by labs affiliated with the University of Pittsburgh or UPMC, or banked for future studies that might involve proteomics, immunology, transcriptomics, or genomics. .

B.2.4.2 Follow-up study visits

All participants will have a blood draw at Day 28 (range 21-35 days). A subset (up to 120) of participants ages 9 -21 will have a blood draw at Day 7 (range 6-9 days).

The amount of blood to be drawn at each timepoint is noted in the Table.

B.2.4.3 Specimen Processing and Sharing with Collaborators

[name] lab at the Rangos Research Building will process all blood specimens for storage and handling following standard protocols by trained study staff. Specimens will be shipped to CDC and CDC's chosen laboratory contractors as well as to other contracted laboratories for processing and analysis.

Flow cytometry results from CDC will be shared with Pitt so that further bioinformatics analyses can be conducted.

B. 3 Laboratory Methods

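### Neither the randomization nor the planned seroconversion comparison accounts for age group or 2019-20 vaccination, although recruitment is organised by both

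*Combined protocol and SAP*

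**What the plan says.** **Allocation.** The Methods paragraph of the opening summary says "Randomization to either LAIV or ccIIV on a 1:1 ratio will be done in blocks of 4". Section B.2.4.1a describes allocation "using a 1:1 computer generated simple randomization scheme" and then adds "Randomization block size will be conducted in sets of four". Simple and blocked randomization are different methods, so the wording needs tidying, but both places point to blocks of four. No stratification factor is named anywhere.

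**Recruitment.** The opening summary says "Efforts will be made to recruit/include children 4-8 years and persons not vaccinated in 2019-20 for comparison of immune response to those previously vaccinated". Section B.2.2 states that about half "of the subjects would be recruited from our returning 2019-2020 vaccinated cohort", and that among the other recruits "we will prioritize persons ages 4-8 years regardless of 2019-20 vaccination status and persons 9-21 years who were not vaccinated".

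**Analyses by prior vaccination.** The opening summary and the Introduction announce such comparisons without a condition. Section C.1 adds that "analyses based on prior 2019-20 vaccine history (none, egg-based, cell-based) will provide additional insight", but only if there is money for the full sample.

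**Adjustment.** Section C adjusts the fold-rise analysis for the pre-vaccination titer. It states no adjustment for seroconversion, the primary endpoint in B.1, and the power basis in C.1 is a plain chi-square test.

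**The concern.** The sample is put together from groups that the protocol itself treats as distinct: returning participants vaccinated in 2019-20, children aged 4-8, and people aged 9-21 who were not vaccinated in 2019-20. The Introduction presents prior vaccine history as something that may shape the response. Blocks of four without strata keep the arms equal in total size but do not keep them alike within these groups. A factor related to the outcome can be handled at allocation, in the analysis, or in both; here neither is stated for seroconversion. At stake are a chance difference between arms that stays in the estimate, some avoidable variance, and less convincing contrasts within the prior-vaccination groups. The opening summary also assumes different drop-out by age (21% under 9, 11% from 9 up), so an age imbalance at entry would carry through into unequal losses.

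**Working it through.** **Inputs from the documents.** Enrollment of 240-260, 16% drop-out and about 200 completers (opening summary); up to 130 per arm (B.2.2); about half the sample from the returning vaccinated cohort (B.2.2); chi-square test, alpha 0.05, effect size 0.2, N=200, power .81 (C.1).

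**Assumptions.** Seroconversion of 50% overall and a 25-point difference between previously vaccinated and unvaccinated participants; the documents give neither. They give no age split either. The 16% overall drop-out is what an equal split would produce, (21+11)/2, but this is not stated. Subgroup shares of 15% to 50% are therefore used below.

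**1. The plan's own figures.** With 1 degree of freedom and noncentrality N·w² = 200 × 0.2² = 8, power is 0.807, which agrees with .81. The other four rows of the table also reproduce. Completers: 240 × 0.84 = 202, in line with about 200.

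**2. Chance imbalance.** For a factor present in half the sample, the 95% range of the difference between arms in its prevalence is 1.96 × √(0.25 × 4/N). At N=240 this is 1.96 × 0.0645 = 0.127, or ±12.7 points. Simulation of 20,000 unstratified allocations in blocks of four gives the chance of a difference of 10 points or more as about 18% at N=200 and 12% at N=260.

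**3. Effect on the arm contrast.** Shift = imbalance × difference in seroconversion by the factor. At the 95% limit: 12.7 × 0.25 = 3.2 points. At the median imbalance: 0.674 × 6.45 = 4.4 points, and 4.4 × 0.25 = 1.1 points.

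**4. Precision at N=200.**
- Unadjusted half-width: 1.96 × √(0.25/100 + 0.25/100) = 0.139, or 13.9 points.
- Share of outcome variance explained by a 25-point factor split 50:50: 0.125²/0.25 = 0.0625.
- Adjusted half-width: 13.9 × √(1 − 0.0625) = 13.4 points.
- To match this without adjustment would take 200/0.9375 = 213 completers.

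**5. Within subgroups.** Chance of a 60:40 or worse split between arms at N=200, from the same simulation, and power for 40% v 60% with equal arms:

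| Subgroup size | Chance of 60:40 or worse | Power at 50:50 |
|---|---|---|
| 100 | 0.6% | 0.516 |
| 67 | 5% | 0.371 |
| 50 | 11% | 0.289 |

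At size 50, a 60:40 split lowers power only from 0.289 to 0.279. At size 30 the chance of such a split is 26%.

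**6. With strata.** Blocks of four within each stratum hold the arms to a difference of at most 2 per stratum at randomization, so at most 4 × 2 = 8 overall with four strata.

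**The case against.** Unstratified permuted blocks are a valid design at this size. Chance imbalance is not bias, and the ordinary standard error already allows for it. The shift of about 3 points is a 95% extreme under an assumed 25-point difference, set against a half-width of 13.9 points and a planning effect of about 20 points (w=0.2, for example 40% v 60%). Adjusting fold rise for the pre-vaccination titer may already absorb part of the prior-vaccination effect. All of this stands, and it keeps the point small. It does not cover seroconversion, for which no adjustment is stated.

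A reader might infer more than the documents support:
- **That the arm comparison is biased or its power overstated.** It is not; the stated power reproduces and does not depend on stratification.
- **That uneven splits are what weaken the subgroup comparisons.** They cost almost no power. Subgroup size is the limit, and stratifying does not change it.
- **That every prior-history analysis is a firm commitment.** The three-level analysis in C.1 depends on funding.
- **That an analysis by age group is planned.** None is stated. Ages 4-8 are prioritised because the first year had too few of them.
- **That vaccination status is always known before allocation.** B.2.2 takes new recruits aged 4-8 whatever their prior status, B.2.4.1a obtains history from records with consent, and randomization follows on consent.

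**Conclusion.** The point holds as a minor one. No stratification factor is named, and the primary seroconversion comparison has no stated adjustment for two factors around which recruitment is organised. The overall comparison remains unbiased and its stated power is unaffected. What is lost is correction of chance imbalance (95% range about ±12.7 points at N=240 for a factor in half the sample) and a little precision (half-width 13.9 v 13.4 points at N=200). The precision figure and the 1- to 3-point shifts rest on the assumed 50% seroconversion and 25-point difference; a weaker factor would make them smaller. The imbalance range needs only the one-half share, which for prior vaccination follows roughly from B.2.2.

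**What to change.** **In section C.** Analyse seroconversion with a model, for example logistic regression reported as a marginal risk difference, that includes arm, age group (4-8 v 9-21) and 2019-20 vaccination (yes v no). Add the same two factors to the fold-rise model beside the pre-vaccination titer. The trial already collects both, so the cost is a few lines of text, and this remains possible after enrollment has closed if it is fixed before the data are compared by arm.

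**If enrollment is still open.** Also run the blocks of four within these four strata, once vaccination status is confirmed from cohort, medical or registry records. The costs are four lists, up to four incomplete blocks, and a check of status before allocation, which will matter most for new recruits aged 4-8. Yes/no strata would not balance egg-based against cell-based prior vaccine, so they would not by themselves secure the three-level comparison in C.1.

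**In B.2.4.1a.** State one randomization method in place of the two terms now used.
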